9.4.1 Efficacy analyses

All efficacy analyses will be performed on the ITT population, unless otherwise specified.

Table 7 - Efficacy analyses

Endpoint	Statistical Analysis Methods

Primary
 
Time to the first occurrence of any of the following clinical events, positively adjudicated by the CEC:
 
 CV death Non-fatal MI Non-fatal stroke 	
The time to the first occurrence of the primary composite CV endpoint event (CV death, non-fatal MI, or non-fatal stroke) will be analyzed using Cox proportional hazards model with treatment (efpeglenatide 4 mg, efpeglenatide 6 mg, placebo), region and randomization strata of current or potential future use of a SGLT2 inhibitor (Current use, Potential future use, Neither current nor potential future use) as the covariates. Participants who receive either 4 mg or 6 mg of efpeglenatide will be combined as one efpeglenatide treatment group when making comparisons using appropriate contrast for the purposes of the primary analysis. The hazard ratio between pooled efpeglenatide and placebo will be estimated along with the associated two-sided 95%CI.
 
The NI with the 1.8 and 1.3 margin will be demonstrated on the primary endpoint if the UB of the two-sided 95% CI is <1.8 and 1.3, respectively.

Endpoint

Statistical Analysis Methods

Kaplan-Meier curves of the cumulative incidence rate will also be provided by treatment groups.

All participants will be followed up to the Study Closeout Visit or death, whichever comes first. The primary analysis will be based on the ITT approach that includes events occurring from randomization to the end of study, even after the participant has discontinued the study treatment. In the ITT approach, all randomized participants will be included and analyzed as randomized.

The analysis will be based on the positively-adjudicated CV endpoint events. Time to the first occurrence of the primary CV event is the time from randomization to the first occurrence of cardiovascular death, non-fatal MI, or non-fatal stroke over the duration of the study (ie, randomization to the study end date inclusive). Participants who have not experienced any of these primary cardiovascular outcomes as positively adjudicated by the CEC during the study will be censored at the last date with available information on the CV outcomes on or before the study end date for the participant.

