### 1.3 DETERMINATION OF SAMPLE SIZE

It is estimated that approximately 4000 participants are needed to obtain approximately 330 participants with a positively adjudicated event for the primary composite cardiovascular endpoint (3-point MACE), based on the following trial design characteristics assumptions:

[figure not shown]
- A recruitment period of approximately 12 months
- Study duration is estimated to be approximately 24 months of follow-up after the last randomized patient, estimated follow-up ranging from 24 to 36 months
- 2% annual early study discontinuation
- Yearly event rate in placebo group: 4.4% for participants not using a SGLT2 inhibitor, and 3.7% for participants using a SGLT2 inhibitor
- Treatment effect of efpeglenatide compared to placebo: 15% risk reduction for participants not using a SGLT2 inhibitor, and a neutral effect for participants using a SGLT2 inhibitor
- 20% of participants using a SGLT2 inhibitor at baseline, and additional 10% participants in placebo group and 5% participants in efpeglenatide group adding a SGLT2 inhibitor during the study period

This will provide:

- 90% power to demonstrate non-inferiority (NI) of efpeglenatide vs placebo with a 1.3 NI margin {upper bound of the 95% CI of the estimated hazard ratio <1.3} for the 3-point MACE (CV death, non-fatal MI or non-fatal stroke)
- >99% power to demonstrate NI with a 1.8 margin

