#### **2.3.4.1 Analysis of primary efficacy endpoint(s)**

##### **2.3.4.1.1 Statistical Hypotheses**

The statistical hypothesis for the primary endpoint of 3-point MACE is to test that efpeglenatide is noninferior (1.8 and 1.3 margin) to placebo at the two-sided 5% alpha level:

- H0: Hazard ratio of efpeglenatide (pooled 4mg and 6mg groups) versus placebo  $\geq 1.8$  vs.  
Ha: Hazard ratio of efpeglenatide versus placebo  $< 1.8$

and

- H0: Hazard ratio of efpeglenatide (pooled 4mg and 6mg groups) versus placebo  $\geq 1.3$  vs.  
Ha: Hazard ratio of efpeglenatide versus placebo  $< 1.3$

The time to the first occurrence of the composite 3-point MACE endpoint (CV death, non-fatal MI, non-fatal stroke) will be analyzed using a Cox proportional hazards model with treatment (efpeglenatide 4 mg, efpeglenatide 6 mg, placebo), region (Norther America, Latin America, Europe, other), and randomization stratum of use of an SGLT2 inhibitor (current use, potential future use, neither current nor potential future use) as the factors. The analyses will be performed by including only events positively adjudicated by the CEC. Participants who receive either 4 mg or 6 mg of efpeglenatide will be combined as one efpeglenatide treatment group when making comparisons using appropriate contrast for the purposes of the primary analysis. The hazard ratio between pooled efpeglenatide and placebo will be estimated along with the associated 2-sided 95% CI. The NI with the 1.8 and 1.3 margin will be demonstrated on the primary endpoint if the upper bound of the 2-sided 95% CI is less than 1.8 and 1.3, respectively.

The time to event will be calculated as date of event as determined by the CEC (or date of censoring) – randomization date +1.

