- Step 1: For each arm, the hazard rate after treatment discontinuation will be generated from the posterior distribution of the parameters in the exponential survival function in subjects who have discontinued treatment but either have MACE event prior to scheduled study closeout visit or have completed study.

Note: the Kaplan-Meier curve based on observed pooled data is nearly a straight line, so constant hazard rate is assumed. So exponential survival function is used for hazard rate for each arm.

- Step 2: The missing event date of scenario 4 will be imputed multiple times by the samples of the hazard rate generated in Step 1. The imputed event date will be censored by the planned study close-out visit date if the imputed event date is after the study close out visit date.

- Step 3: In each imputation, the imputed dataset will be analyzed by the same Cox proportional hazards model as the primary analysis.
- Step 4: The results of the above analyses will be combined using Rubin's formula
- A tipping point analysis will be performed, where time to events will be imputed by using the same multiple imputation method as described above (step 1-4) and vary the hazard rates for subjects not complete study and have missing MACE event. The goal of the analysis is to find the scenarios where the result from the primary endpoints analyses will be “tipped”, i.e., the conclusion of non-inferiority will change. More specifically, a grid-search with hazard rates for the efpeglenatide group increased by an increment (e.g. 1, 1.1, 1.2, 1.3, 1.4, 1.5, 1.6, ...) will be implemented to explore the plausibility of missing data assumptions. A proper range of the hazard rates will be searched to estimate the point where the upper bound of 95% CI for the hazard ratio exceeds 1.3, and 1.8 respectively, when the corresponding comparison fails to declare statistical significance for non-inferiority.

SAS pseudo-codes is provided in [Appendix D](#).

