#### **2.3.4.2 Analyses of secondary efficacy endpoints**

If the NI with the 1.8 and 1.3 margin is demonstrated on the primary endpoint, the superiority of pooled efpeglenatide vs placebo for the primary endpoint will be tested in a hierarchical order. The superiority will be claimed if the UB of the 2-sided 95% CI of hazard ratio is less than 1. The nominal p-value using the log-rank test (stratified by randomization stratum of use of an SGLT2 inhibitor) will also be calculated.

The secondary time to event endpoints will be analyzed using the same Cox proportional hazards model as used for the analysis of primary endpoint described above. The analyses will be performed by including events positively adjudicated by the CEC for cardiac events, and events as reported by investigator for renal events. The hazard ratios between pooled efpeglenatide and placebo will be estimated along with the associated 2-sided 95% CIs. See [Appendix C](#) for the censoring rule.

Kaplan-Meier curves of the cumulative incidence rates will be provided by treatment groups. The incidence rate per 100 patient-years will be reported. The p-value using the log-rank test (stratified by randomization stratum of use of an SGLT2 inhibitor) will also be calculated.

Individual components of the secondary endpoints will be analyzed using the same Cox proportional hazards model described above.

In addition, the total number of events sent for adjudication and positively adjudicated will be summarized as well as the concordance rate between investigator opinion and adjudication by the CEC for each cardiac event type.

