    Scens=1*exp(-1*(adt-trtedt)*_lbdcur);  ** compute 1-
survival at censored time;
    Fcens=1-Scens;
    u=Fcens+ranuni(14828)*(1-Fcens);  ** simulate uniform r.v
from Fcens to 1;
    imp_censor_date =trtedt - (log(1-u))/_lbdcur;
    format imp_censor_date YYMMDD10.;
```

```
if imp_censor_date > scv then
    do; imp_censor_date = scv;
        imp_censor=0; /*imp-censor: 1 event, 0 further
censored*/
    end;
else
    do; imp_censor=1; end;

run;
/*observed data no missing data first: sce2 and sce3*/
data complete;
    set sce1 sce2 sce3;
    imp_censor=cnsrn;
    imp_censor_date=adt;
    _input_=0;
    do i = 1 to 100;
        _input_=_input_+1;
        output;
    end;
run;

/*combine observed data with imputed data (sce4 with missing data)
*/
data imputed;
    set complete tempdata;
    imp_time=imp_censor_date- rfstdt;
    if armn=1 then armpool=1; else armpool=2; /*armpool combine
treatment group 4mg and 6mg in one group*/
    drop loglike logpost u iteration;
run;

/*proc print data=imputed (obs=1000);
var armn armpool;
run; */

proc sort data=imputed;
    by _input_ armpool;
run;

proc phreg data = imputed;
    by _input_;
    class armpool (ref=first) region1 STRATUM;
    model imp_time*imp_censor(0)=armpool region1 STRATUM/risklimits
rl;
    ods output ParameterEstimates=_es;
run;
*****proc sort data=_es;
    by parameter ClassVal0;
run;
proc mianalyze data=_es alpha=0.05;
```

[figure not shown]
```
by Parameter ClassVal0;
  modeleffects Estimate;
  STDERR StdErr;
  ods output ParameterEstimates = _es_mianal;
run;

data mihr;
  set _es_mianal;
  where parameter='armpool'; /*only keep hazard ratio of
treatment*/
  LogHR_mi=Estimate;
  HR_mi=exp(Estimate);
  HR_LCL_mi=exp(LCLMean);
  HR_UCL_mi=exp(UCLMean);
  Delta=&delta1;
  keep Parameter ClassVal0 LogHR_mi HR_mi HR_LCL_mi HR_UCL_mi
Probt delta;
  rename Probt=Probt_mi;

run;
```

Signature Page for [REDACTED]  
efc14828-16-1-9-sap

Approve & eSign

Approve & eSign

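### The contrast behind the deciding pooled hazard ratio has no stated weights, and Appendix D fits a different treatment term from the primary model it is said to repeat

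*SAP*

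**What the plan says.** **Primary model.** SAP 2.3.4.1.1 lists treatment as a three-level factor, with region and SGLT2 stratum. The doses are then "combined as one efpeglenatide treatment group when making comparisons using appropriate contrast for the purposes of the primary analysis". Protocol 9.4.1, Table 7, has the same three-level factor and the same phrase ("combined as one efpeglenatide treatment group when making comparisons using appropriate contrast"), and so does the synopsis. No coefficients appear in these places, in SAP 2.3.4.4 (multiplicity) or in SAP Appendix B.

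**What it decides.** SAP 2.3 restricts formal testing to pooled efpeglenatide against placebo. Non-inferiority is shown if the "upper bound of the 2-sided 95% CI is less than 1.8 and 1.3, respectively". For 3-point MACE, "The superiority will be claimed if the UB of the 2-sided 95% CI of hazard ratio is less than 1". Expanded MACE and nephropathy follow in the hierarchy with the same model.

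**Missing-data analysis.** Step 3 in SAP 2.3.4.1.3 (Assessment of missing data) says "the imputed dataset will be analyzed by the same Cox proportional hazards model as the primary analysis". The tipping-point analysis reuses those steps. Appendix D recodes treatment to a variable that a code comment describes as putting 4 mg and 6 mg in one group, and then fits "model imp_time*imp_censor(0)=armpool region1 STRATUM/risklimits".

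**The concern.** A three-level model with a contrast and a two-level pooled term are different estimators. The first gives a weighted average of two log hazard ratios. The second gives one hazard ratio for the merged group, close to the arithmetic mean of the dose hazard ratios under equal dose allocation. They agree only when the doses act alike, and even then only up to sampling noise.

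Two things are at stake. First, the weights behind the single bound that decides every formal test are left to whoever writes the program, although several choices fit the text. Second, the imputation and tipping-point results are meant to be read against the primary result. If the treatment term also changes, the effect of the missing-data assumptions cannot be separated from the effect of the estimator.

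**Working it through.** **1. The plan's own figure.** SAP 1.3 states "90% power to demonstrate non-inferiority (NI) of efpeglenatide vs placebo with a 1.3 NI margin". Inputs from the same section: 330 events; yearly placebo rates of 4.4% (no SGLT2 inhibitor) and 3.7% (with one); 15% risk reduction without an SGLT2 inhibitor and none with one; 20% baseline use, plus 10% (placebo) or 5% (efpeglenatide). Allocation is 2:1 pooled to placebo. Counting the added use in full:

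- placebo: 0.70 × 4.4 + 0.30 × 3.7 = 4.19% a year
- efpeglenatide: 0.75 × 4.4 × 0.85 + 0.25 × 3.7 = 3.73% a year
- HR = 3.73 / 4.19 = 0.89
- power = Φ(√(330 × 1/3 × 2/3) × ln(1.3/0.89) − 1.96) = Φ(8.564 × 0.3789 − 1.96) = Φ(1.285) = 90%

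The 90% reproduces. It rests on one pooled effect and says nothing about how the doses are averaged.

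**2. The candidate estimators.** Let d0, d4 and d6 be first-event counts, with equal follow-up in equal-sized arms and no covariates.

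- Equal-weight contrast: b = ½[ln(d4/d0) + ln(d6/d0)]; variance = ¼(1/d4 + 1/d6) + 1/d0
- Two-level term: b = ln[(d4 + d6)/(2·d0)]; variance = 1/(d4 + d6) + 1/d0
- Event-weighted contrast: b = w·ln(d4/d0) + (1 − w)·ln(d6/d0), w = d4/(d4 + d6); variance as for the two-level term

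The upper bound is exp(b + 1.96·SE).

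**3. Expected counts at a combined-group HR of 0.89.** Here d0 = 330/2.78 = 118.7 and d4 + d6 = 211.3. The two-level SE is 0.1147 and its bound is 1.114. The ratio of the two doses' hazard ratios is an assumption; the documents give no dose-specific effect.

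| HR6/HR4 | HR4, HR6 | Equal-weight bound ÷ two-level bound | Event-weighted bound ÷ two-level bound |
|---|---|---|---|
| 1.0 | 0.89, 0.89 | 1.000 | 1.000 |
| 0.9 | 0.94, 0.84 | 0.999 | 1.001 |
| 0.8 | 0.99, 0.79 | 0.994 | 1.006 |
| 0.7 | 1.05, 0.73 | 0.986 | 1.016 |
| 0.6 | 1.11, 0.67 | 0.971 | 1.032 |

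For example, at 0.8 the equal-weight log HR shifts by −0.0062 and the SE rises from 0.1147 to 0.1150, so the ratio is exp(−0.0062 + 1.96 × 0.00026) = 0.994.

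**4. Simulated trials.** 4000 patients, stop at 330 events, 12-month accrual, 2% yearly dropout, stratified permuted blocks, region and stratum in the model, 8000 trials per scenario. Block size, covariate shares and effects, and dose HRs were assumed.

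- Doses alike: mean bound ratio (equal-weight ÷ two-level) 0.998. The gap comes from chance differences between the dose arms.
- Doses 1.0/0.78, 1.15/0.85 and 1.5/1.1 (4 mg/6 mg): mean ratio 0.988 to 0.992.
- Over seven scenarios and margins 1.0 and 1.3, equal weights and the two-level term gave different decisions 850 times, each a success for the contrast only. Event weights differed from the two-level term 941 times, each a success for the two-level term only.
- Under simple randomisation, 2 of 115 discordant decisions went against the equal-weight contrast.

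**5. Error rate.** Multinomial draws of 330 events with the step 2 formulas, 400,000 runs, margin 1.3, one-sided:

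- Doses 1.3/1.3: 2.7% for both equal weights and the two-level term.
- Doses 1.0/1.6 (arithmetic mean 1.3): 4.4% for equal weights, 2.7% for the two-level term.
- Doses 1.0/1.69 (geometric mean 1.3, the contrast's own null): 2.7% for equal weights.
- Doses 0.9/1.88 (geometric mean 1.3): 2.7% for equal weights.

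**6. Effect on the tipping point.** Suppose the primary bound were 1.290 from an equal-weight contrast. With a bound ratio of 0.988, the two-level model on the same data gives 1.290/0.988 = 1.306. The result would appear tipped at 1.3 before any event was imputed.

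**The case against.** **Appendix D is sample code for a supportive analysis and decides nothing.** This stands. The deciding model, three-level Cox plus a contrast, is stated consistently in both documents. The mismatch does not create a second deciding analysis. It affects how the missing-data results compare with the primary one.

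**The primary text also speaks of one combined group, so Appendix D might be the intended reading.** That is possible, but the three-level factor and the contrast would then have no role. The text leaves the question open.

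**The effect is small unless the doses diverge, and SAP 1.3 plans a single effect.** This also stands. At about 0.2% on the bound, decisions would rarely change.

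**A stronger reading.** A reader might infer that the open contrast favours efpeglenatide or raises the type I error. The documents do not support this. The direction follows from assuming equal weights, and event weights reverse it. With doses 0.85/1.22, non-inferiority at 1.3 succeeds in about 54% of runs with equal weights, 50% with the two-level term and 43% with event weights. The 4.4% in step 5 arises only if the null is read as an arithmetic-mean hazard ratio. SAP 2.3.4.1.1 tests whether efpeglenatide is "noninferior (1.8 and 1.3 margin) to placebo at the two-sided 5% alpha level", and it names the pooled groups without fixing an averaging scale. At its own null the equal-weight contrast rejects 2.7% of the time, the same as the two-level term at its null.

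**Conclusion.** The point holds in a limited form. Step 3 and Appendix D contradict each other about the model, and the weights of the deciding contrast are not pre-specified. The two-level bound and an equal-weight contrast differ by about 0.2% when the doses act alike. They differ by about 1% in the simulated unequal-dose cases, and by up to about 3% at a dose hazard-ratio ratio of 0.6. These sizes rest on assumed dose effects and proportional hazards within each dose; the direction rests on the weights. The primary test is valid for whichever average it targets, so this is not an error-rate finding. The practical consequence is that the delta=1 and tipping-point results cannot be compared cleanly with the primary result.

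**What to change.** Keep the protocol's three-level model. In SAP 2.3.4.1.1, state the contrast weights, for example (1/2, 1/2, -1) on 4 mg, 6 mg and placebo, and say that the contrast tests the average log hazard ratio. State that the same contrast is used for every step of the hierarchy.

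In Appendix D, replace the pooled term with the three-level treatment factor and an estimate statement for that contrast, and pass the contrast estimate and its standard error to the Rubin combination. When rewriting the code, also check the arm coding: the variable list gives control the value 0, while the recode treats 1 as placebo.

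The cost is one sentence and one model and estimate statement before database lock. Events and the stated 90% power are unchanged: at HR 0.89, simulated power for the 1.3 margin is 89.9% with the equal-weight contrast and 89.6% with the two-level term. Making the two-level term the primary model would also remove the mismatch, but it departs from the protocol's stated model and is not needed.

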##### **2.3.4.1.2 Censoring rule**

Patients will be right-censored at the last date with information available on the CV outcomes if they have not experienced any positively-adjudicated component of the primary composite CV events on or before their end of study visit. Specifically, the censoring date is defined as follows:

- Patients who completed the study will be censored at their scheduled last study visit date (study close-out visit date or final follow-up visit date)
- Patients who died before completing or discontinuing the study (ie, death reported on the Completion of End of Study form) will be censored at their date of non-CV death

- Patients who discontinued the study will be censored at their later of study discontinuation date or latest date with cardiovascular efficacy endpoint information (MI/UA, heart failure, cerebrovascular event, admission to hospital/emergency room, coronary procedure, or cardiac biomarkers as collected in eCRF) collected. For more details of censoring rule, please refer to [Appendix C](#).

Kaplan-Meier curves of the cumulative incidence rate will be provided by treatment groups over on-study efficacy period (from randomization to end of study date). The incidence rate per 100 patient-years (calculated by 100 \* number of patients with events / sum of time at risk (days) over all patients/365.25) will be reported. For patients with an event, patient-year is time from randomization to first event; for patient without any event, patient-year is from randomization to censoring date.

Underlying assumptions of the Cox proportional hazards model will be checked by visual inspection of the Kaplan-Meier plots (log(-log(survival)) vs log(survival time)).

Individual components of the primary endpoints will be analyzed using the same Cox proportional hazards model described above. Censoring rules described above will be used, and for components other than CV death, patients who died before completing or discontinuing the study will be censored at date of death (i.e. CV or non-CV death). See [Appendix C](#) for specific censoring rules.

#### 2.3.4.1.3 Sensitivity analysis

- The primary analysis of the primary endpoint will be repeated by censoring the events at the time a participant starts treatment with a SGLT2 inhibitor (for participants who were not receiving a SGLT2 inhibitor at baseline) or stops treatment with a SGLT2 inhibitor (for participants who were already receiving an SGLT2 inhibitor at baseline).
- The primary analysis of the primary endpoint will be repeated using the ITT analysis set, by excluding deaths adjudicated as 'undetermined cause of death' by the CEC.
- The primary analysis of the primary endpoint will be repeated by including only events from randomization to last IMP administration date + 30 days or patient's last study visit date, whichever is earlier. For patient not having a primary endpoint during this period, the patient will be right-censored at the earlier date of last IMP administration date + 30 days, and patient's censoring date defined above.
- If discrepancy in stratum assignment between IRT and eCRF occurred in more than 5% of patients, the primary analysis will be repeated using the actual use of SGLT2 inhibitor at baseline (yes, no).

[figure not shown]
#### Assessment of missing data

For patients who discontinued study but no MACE event was positively adjudicated by scheduled study closeout visit, the missing data are events that may occur after a patient is censored (the later of the patient's study discontinuation date and the last date they have information on CV efficacy endpoint for patients who discontinued the study).

[figure not shown]
Reasons for censoring (including non-CV death, completed study, and study discontinuation reasons) will be summarized. For patients who discontinued the study, the time from censoring date to planned study close-out visit date will be summarized to show the magnitude of missing information.

Subjects prematurely and permanently discontinuing IMP, for other reason than death, prior to study end could have a different event and hazard rate from those who stay on IMP throughout the study, and their corresponding dropout could be considered informative. This subgroup can be divided into subjects with information and subjects with missing information regarding primary MACE endpoints, see figure below.

Diagram showing subjects divided into subgroups related to missing information about MACE.

Subjects with information related to the MACE endpoint events (either discontinued study but have MACE prior to scheduled study closeout visit, or completed the study) will be used to impute data in subjects without MACE endpoints (discontinued study and no MACE event reported through third party data by scheduled study closeout visit). Subjects who developed MACE prior to the IMP discontinuation are included for imputation and their time to MACE data will be used for the imputation modeling. With these subjects included, the model estimate of hazard should fully reflect the potential hazard of the subjects with missing outcome. More specifically, subjects from below scenarios 2 and 3 will be used to impute the missing data of scenario 4 of the same treatment arm:

Note:

1. SCV: study close-out visit;
2. MACE censoring date of scenario 4 is the later of study discontinuation date or latest date with CV event information collected

The following supportive analyses will be performed to evaluate how the primary efficacy results could be influenced by different assumptions about the missing data. In particular, a 4-step approach will be used:

- Step 1: For each arm, the hazard rate after treatment discontinuation will be generated from the posterior distribution of the parameters in the exponential survival function in subjects who have discontinued treatment but either have MACE event prior to scheduled study closeout visit or have completed study.

Note: the Kaplan-Meier curve based on observed pooled data is nearly a straight line, so constant hazard rate is assumed. So exponential survival function is used for hazard rate for each arm.

- Step 2: The missing event date of scenario 4 will be imputed multiple times by the samples of the hazard rate generated in Step 1. The imputed event date will be censored by the planned study close-out visit date if the imputed event date is after the study close out visit date.

- Step 3: In each imputation, the imputed dataset will be analyzed by the same Cox proportional hazards model as the primary analysis.
- Step 4: The results of the above analyses will be combined using Rubin's formula
- A tipping point analysis will be performed, where time to events will be imputed by using the same multiple imputation method as described above (step 1-4) and vary the hazard rates for subjects not complete study and have missing MACE event. The goal of the analysis is to find the scenarios where the result from the primary endpoints analyses will be “tipped”, i.e., the conclusion of non-inferiority will change. More specifically, a grid-search with hazard rates for the efpeglenatide group increased by an increment (e.g. 1, 1.1, 1.2, 1.3, 1.4, 1.5, 1.6, ...) will be implemented to explore the plausibility of missing data assumptions. A proper range of the hazard rates will be searched to estimate the point where the upper bound of 95% CI for the hazard ratio exceeds 1.3, and 1.8 respectively, when the corresponding comparison fails to declare statistical significance for non-inferiority.

SAS pseudo-codes is provided in [Appendix D](#).

